STUDY PROTOCOL

Official Title: *Effect of Menstrual Cycle on Postoperative Sensitivity and Rebound Pain in Posterior Composite Restorations: A Double-Blind Split-Mouth Clinical Study*

Unique Protocol ID: FIRAT-DENTISTRY [name]-001

NCT ID:

Date: 01.09.2022

Principal Investigator: [name], PhD, Assistant Professor

Affiliation: Firat University, Faculty of Dentistry, Department of Restorative Dentistry, Elazig, Turkey

✉@ mail [contact]

📞 [contact]

Study Objectives:

- **Primary Objective:** To evaluate the effect of menstrual cycle phases on postoperative sensitivity (POS) following direct posterior composite restorations.
-
- **Secondary Objective:** To assess whether menstrual cycle phases influence the incidence or severity of rebound pain (RP) after inferior alveolar nerve block (IANB).

Study Design:

- **Type:** Double-blind, split-mouth, randomized clinical trial
- **Study Groups:**
 - **Menstrual Phase Group (MPG):** Restorations performed during **days 1-3** of menstruation.
 - **Ovulatory Phase Group (OPG):** Restorations performed on **days 11-16**, depending on cycle length.
- **Number of Participants:** 35 women, each receiving two restorations
- **Total:** 70 restorations).
- **Masking(Blinding):**
 - The operator performing the restorations and the researcher assessing the outcomes were blinded to menstrual cycle phases.

Eligibility Criteria:

Inclusion Criteria:

- Women aged 18-45 years
- Regular menstrual cycles (26-32 days)
- No hormonal contraceptive use
- Vital posterior mandibular molar teeth requiring restorative treatment
- Good oral and periodontal health

Exclusion Criteria:

- Irregular menstrual cycles or hormonal disorders
- Pregnancy or lactation
- Use of analgesics or anti-inflammatory drugs within 48 hours before treatment
- Severe periodontal disease or need for endodontic treatment

Interventions & Procedures:

- **Anesthesia:** Inferior alveolar nerve block (**IANB**) with articaine hydrochloride with epinephrine (1:100,000)
- **Restorative Material:** Clearfil Universal Bond Quick (Kuraray, Japan) and Clearfil Majesty Posterior (Kuraray, Japan) .
- **Postoperative Sensitivity (POS) Assessment:**
 - VAS (0-10) measured at Day 1, Day 2, and Day 3 after restoration.
- **Rebound Pain (RP) Assessment:**
 - VAS (0-10) measured at Hour 4, Hour 8, and Hour 12 after anesthesia resolution.

Statistical Analysis:

- **Cochran's Q test** for intragroup comparisons
- **McNemar's test** for post-hoc analysis

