- **Chi-Square test or Fisher's Exact Test** for intergroup comparisons
- **Bonferroni correction** for multiple comparisons
- **Significance Level:** $p < 0.05$

Ethical Approval:

- Non-Interventional Research Ethics Committee of Firat University
- Reference No: 2022/08-07
- **ClinicalTrials.gov Registration No:** has not been created yet

Date of creation: 01.09.2022

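### The between-phase comparison is planned as an unpaired Chi-Square/Fisher test although each woman supplies one restoration per phase, and nothing says how missed readings or a missed second visit are handled

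*Combined protocol and SAP*

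**What the plan says.** Under Study Design the trial is a "Double-blind, split-mouth, randomized clinical trial" with "35 women, each receiving two restorations", in all "70 restorations". One restoration falls in days 1 to 3 of menstruation; for the other group the entry reads "Restorations performed on days 11-16, depending on cycle length". The two cannot share a visit.

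Under Interventions & Procedures, each restoration gives three readings per endpoint. Postoperative sensitivity (POS) is "VAS (0-10) measured at Day 1, Day 2, and Day 3 after restoration", and rebound pain (RP) is "VAS (0-10) measured at Hour 4, Hour 8, and Hour 12 after anesthesia resolution".

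The Statistical Analysis section lists "Cochran's Q test for intragroup comparisons", McNemar's test as post-hoc, "Chi-Square test or Fisher's Exact Test for intergroup comparisons", a Bonferroni correction and a 0.05 level. It gives no rule for missing readings or for a woman treated only once, no analysis set, no dropout allowance, and no VAS cut-off for these binary tests.

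**The concern.** The primary objective is a comparison between two phases, and every woman contributes to both. Chi-Square and Fisher assume that the two sets of restorations come from different people. When a woman's two outcomes are positively correlated, the unpaired test overstates the variance of the difference. It then rejects too rarely and gives up the power that a split-mouth design is meant to provide.

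Incomplete data add a second problem. Cochran's Q needs all three readings of a phase, so one gap removes the woman from that phase's test. Chi-Square/Fisher uses whoever has a reading at a given time, so a woman who misses her second visit stays in one phase with no partner in the other. The within-phase and between-phase results can then rest on different women. If the pain of the first restoration influences return, the phase contrast may also be biased.

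**Working it through.** **Inputs.** From the protocol: 35 women, two restorations each, three readings per endpoint per restoration, level 0.05. Not in the protocol, so assumed with ranges: incidence, within-woman correlation φ, missing-reading rate m, non-return rate d, VAS SD and strength of dropout.

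**1. The plan's own figure.** 35 × 2 = 70 agrees. The 35 cannot be re-derived, because no power, effect size, SD or rate is given.

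**2. Cost of ignoring the pairing, complete data.** With n pairs, the true variance of the difference in proportions is [p1q1 + p2q2 − 2φ√(p1q1p2q2)]/n. The unpaired test uses 2p̄q̄/n.

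- No effect, incidence 0.4, φ = 0.4: true SE = √(0.48 × 0.6/35) = 0.0907. Unpaired SE = √(0.48/35) = 0.1171, so the cut-off is 1.96 × 0.1171 = 0.2295. Then 0.2295/0.0907 = 2.53, a two-sided error of 1.1%.
- 0.5 against 0.3, φ = 0.4: √(0.25 × 0.21) = 0.2291; true SE = √[(0.46 − 0.8 × 0.2291)/35] = 0.0889. Unpaired: (0.2295 − 0.2)/0.0889 = 0.33, power 37%.
- McNemar, same case: both positive = 0.15 + 0.4 × 0.2291 = 0.2417; discordant = 0.2583 + 0.0583 = 0.3167 (from unrounded values); cut-off = 1.96√(0.3167/35) = 0.1864; (0.1864 − 0.2)/0.0889 = −0.15, power 56%.

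A simulation of 40,000 trials of 35 pairs agrees to within about a percentage point:

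| φ | Type I, unpaired | Type I, McNemar | Power, unpaired | Power, McNemar |
|---|---|---|---|---|
| 0 | 4.8% | 5.0% | 39% | 39% |
| 0.2 | 2.8% | 4.6% | 38% | 46% |
| 0.4 | 1.1% | 4.4% | 36% | 57% |
| 0.6 | 0.2% | 4.7% | 33% | 81% |

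**3. Women kept by Cochran's Q.** Expected number per phase = 35(1 − m)³.

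- m = 5%: 35 × 0.857 = 30.0. m = 10%: 35 × 0.729 = 25.5.
- With non-return and balanced order, multiply by (1 − d/2): 30.0 × 0.95 = 28.5 at d = 10%, and 25.5 × 0.90 = 23.0 at d = 20%.

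**4. Bias from non-return, binary scale.** Incidence 0.4 in both phases, φ = 0.4, all women in the same phase order; 40% fail to return after sensitivity and 5% otherwise.

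- Joint probability of sensitivity at both = 0.16 + 0.4 × 0.24 = 0.256. Second-visit incidence is 0.256/0.4 = 0.64 after sensitivity and 0.144/0.6 = 0.24 otherwise.
- Returners: 0.4 × 0.60 = 0.24 and 0.6 × 0.95 = 0.57, total 0.81. Their second-visit incidence is (0.24 × 0.64 + 0.57 × 0.24)/0.81 = 0.359.
- Chi-Square contrast, first minus second: 0.400 − 0.359 = +0.041. Complete pairs: 0.24/0.81 − 0.359 = −0.062. Likelihood: 0.400 − (0.4 × 0.64 + 0.6 × 0.24) = 0.
- With order balanced 1:1, all three are 0 when there is no effect, and the bias is at most 0.009 at 0.5 against 0.3.

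**5. Bias from non-return, VAS scale.** Simulated normal pairs, SD 2, correlation 0.3 to 0.7, 10% to 20% non-return depending on the first score, same order for all, no true effect.

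- Log-odds slope 0.25 per VAS point: absolute bias 0.03 to 0.14. Slope 1: about 0.08 to 0.37. Available-case and complete-pair estimates err in opposite directions. A likelihood estimate is within 0.01 of zero.
- Bias scales with 2f − 1, where f is the share starting in the same phase. At f = 0.6 the maximum is 0.2 × 0.37 = 0.07.
- For scale, the paired SE at n = 35 is 2√(2(1 − ρ)/35): 0.40 at correlation ρ = 0.3, 0.26 at ρ = 0.7.

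**6. If non-return depends on unseen second-visit pain.** In a separate VAS simulation at n = 35 (same order, correlation 0.5), bias is 0.42 for available cases, 0.21 for complete pairs and 0.32 for the mixed model.

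**The case against.** A reader might infer that deletions by Cochran's Q and McNemar distort the phase contrast, and that a likelihood model cures this. The documents do not support that reading.

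- Cochran's Q is listed for comparisons within a group, and McNemar apparently follows it as the post-hoc test. Their deletions affect time comparisons within a phase. McNemar loses only the incomplete pair. Chi-Square/Fisher drops no recorded reading at a given time.
- The upper bias figures need every woman to have the same phase order. The protocol calls the trial randomized without saying what is randomized, so neither a common order nor a balanced one can be assumed.
- Slope 1 is very steep: between women at −1 and +1 SD (4 VAS points) it is an odds ratio of e⁴, about 55. Slope 0.25 gives e¹, about 2.7.
- With a common order, phase and visit order are collinear, so a model containing both cannot estimate the phase effect.
- A model cannot recover visits that never took place. Its precision in the simulations was close to that of complete pairs. It is unbiased only if dropout depends on observed scores and the model is correct.
- A linear model on the VAS changes the outcome scale and meets skewed data with many zeros.

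All of this stands, and it limits the missing-data part. None of it answers the pairing defect, which needs no missing data at all. It could be said that McNemar might also be used between phases, but the plan assigns that comparison to Chi-Square/Fisher.

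**Conclusion.** The point holds for the pairing. The listed between-phase test ignores the split-mouth structure, and this is certain from the text. The size rests on assumed incidence and correlation: at φ = 0.4, about 1% type I error where 5% is intended and roughly 20 percentage points of power lost. At zero correlation nothing is lost; at 0.6 the loss is nearly 50 points. The error is towards missing a real effect, not towards false positives.

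The missing-data part holds in a narrower form. The plan is silent on gaps, Cochran's Q would lose women from the within-phase tests, and non-returners would be counted in one phase only. Bias in the phase contrast is possible but conditional on pain-related non-return together with unbalanced order, or to a small degree a real phase effect. The documents give no rate from which to fix its size.

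**What to change.** Make the main between-phase analysis a paired one that uses every available reading. One suitable form is a linear mixed model per endpoint (POS, RP) on the VAS, with these features:

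- phase, time and phase-by-time as fixed effects, and woman and restoration within woman as random effects;
- women with only one restoration included;
- confidence intervals from a bootstrap by woman, because of skew and zeros;
- visit order added only if both phase orders occur.

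If a binary outcome is kept, state the VAS cut-off and replace Chi-Square/Fisher between phases with McNemar, or with a GEE or mixed logistic model clustered by woman.

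State how missed readings and missed second visits are handled. Give the complete-pair result and a sensitivity analysis for dropout that depends on unobserved pain. Report the phase order, the number of complete pairs and the number of women with full readings beside 35 and 70.

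The cost is analysis wording, a little more programming and model assumptions to check. No visit, procedure or sample size changes.

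### The phase comparison, which is what both objectives ask for, is given to an unpaired test, while the matched-data tests go to change over time within a phase

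*Combined protocol and SAP*

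**What the plan says.** Under Study Objectives, the primary aim is "To evaluate the effect of menstrual cycle phases on postoperative sensitivity (POS) following direct posterior composite restorations". The secondary aim asks the same phase question about rebound pain, its incidence or severity. Under Study Design, the two groups are the two cycle phases, the design is split-mouth, and 35 women each receive two restorations.

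Pain is scored on a 0-10 VAS at Days 1, 2 and 3 for postoperative sensitivity, and at Hours 4, 8 and 12 for rebound pain.

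Under Statistical Analysis:

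- Cochran's Q is listed "for intragroup comparisons".
- "McNemar's test" is listed "for post-hoc analysis", without saying which pairs it compares.
- Chi-Square or Fisher's exact test is listed "for intergroup comparisons".
- Bonferroni is listed "for multiple comparisons", with no family defined.

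The section names no primary test and no primary time point.

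**The concern.** Since the groups are the phases, an intragroup test works inside one phase, and the only repeated factor there is time. Cochran's Q therefore asks whether the proportion with pain changes over Days 1-3 or Hours 4-12. That can happen identically in both phases, so the answer does not bear on phase.

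Both Cochran's Q and McNemar are tests for matched data. If both are used for time, the comparison that the split-mouth design was built for is left to a test that assumes two independent samples of 35. When a woman's two teeth tend to respond alike, that test overstates the variance of the phase difference. It then rejects too rarely and wastes the precision gained by pairing. With only 35 pairs, that loss matters.

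**Working it through.** **Plan's own figure.** 35 women x 2 restorations = 70, as stated. The choice of 35 cannot be reproduced, because no event rate, effect size or power is given.

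**Which test meets which question.**

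| Question | Data structure | Test in the plan |
|---|---|---|
| Change over time within a phase (neither objective) | same tooth, three times | Cochran's Q, then McNemar (matched) |
| Menstrual versus ovulatory (both objectives) | same woman, two teeth | Chi-Square or Fisher (unmatched) |

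**Inputs.** From the documents: n = 35 pairs and alpha 0.05. Assumed: two-sided testing, incidence 40% in both phases (no effect) or 40% versus 20% (effect), and a latent-normal within-woman correlation ρ of 0, 0.3, 0.5 or 0.7.

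**False-positive rate by hand.** With equal incidence p in both phases, the unpaired test takes the variance of the difference as 2p(1-p)/n. The true variance is 2p(1-p)(1-φ)/n, where φ is the correlation of the two yes/no outcomes. The real false-positive rate is therefore about 2[1 - Φ(1.96/√(1-φ))]. At p = 0.4 and ρ = 0.5, φ = 0.33, so 1.96/√0.67 = 2.39 and the rate is 1.7%.

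**Power by hand, 40% versus 20%, ρ = 0.5.** The discordant cells are 0.262 and 0.062, which sum to 0.324.

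- True SD of the difference: √[(0.324 - 0.2²)/35] = 0.0901.
- Chi-square needs a difference of 1.96 x √(2 x 0.3 x 0.7/35) = 0.2147. Power ≈ 1 - Φ[(0.2147 - 0.2)/0.0901] = 43.5%.
- Asymptotic McNemar needs 1.96 x √(0.324/35) = 0.1886. Power ≈ 1 - Φ[(0.1886 - 0.2)/0.0901] = 55%.

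**Full enumeration.** I summed the multinomial probabilities of all tables with 35 pairs, for one time point at 0.05 before any Bonferroni correction.

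False-positive rate, 40% in both phases:

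| ρ | Chi-square | Fisher | Exact McNemar | Mid-p McNemar | Asymptotic McNemar |
|---|---|---|---|---|---|
| 0 | 4.84% | 2.80% | 2.93% | 4.74% | 5.00% |
| 0.3 | 2.85% | 1.47% | 2.61% | 4.50% | 4.54% |
| 0.5 | 1.64% | 0.75% | 2.37% | 4.25% | 4.30% |
| 0.7 | 0.63% | 0.24% | 2.00% | 3.96% | 4.35% |

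Power, 40% versus 20%:

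| ρ | Chi-square | Fisher | Exact McNemar | Mid-p McNemar | Asymptotic McNemar |
|---|---|---|---|---|---|
| 0 | 45.4% | 35.7% | 34.7% | 43.0% | 43.4% |
| 0.3 | 44.8% | 34.3% | 39.8% | 49.1% | 49.2% |
| 0.5 | 44.1% | 32.9% | 45.4% | 55.4% | 55.5% |
| 0.7 | 43.2% | 31.0% | 54.3% | 65.3% | 66.2% |

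The form of McNemar matters. The exact version beats chi-square clearly only at the highest correlation and loses to it at 0.3. The mid-p and asymptotic versions are ahead from 0.3 upwards.

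**The case against.** The best defence is that the plan does contain a direct phase comparison, the Chi-Square or Fisher line, and that its error is on the safe side: with positive correlation it produces fewer false positives. Tests over time are also common secondary analyses and not wrong in themselves. All of this stands. The plan does not lack a phase test, and the time tests need not be deleted. But a test that is conservative because it ignores the pairing still costs power, and a non-significant result from it would be hard to interpret. It is also fair to say that the use of McNemar for time pairs is inferred from its place as the follow-up to Cochran's Q and is not stated.

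Two stronger readings are tempting, and the documents support neither.

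1. **That the plan will declare a phase effect when pain changes significantly in one phase and not in the other.** That rule would be poor. In simulations with 35 women and identical phases, exactly one of the two Cochran's Q tests reached 0.05 in about 7% to 50% of trials, depending on the assumed rates and correlations (about 10% when incidence is flat over time). But nothing in the plan states such a rule, so these figures describe a possible misreading and not a planned analysis.
2. **That the time tests drain power from the phase comparison through Bonferroni.** There could be 16 within-phase tests (2 outcomes x 2 phases x [1 Cochran's Q + 3 McNemar]) and 6 phase tests (2 outcomes x 3 times). One family of 22 would use 0.05/22 = 0.0023, against 0.05/6 = 0.0083 for the phase tests alone. The plan does not define the family, so this cost may not arise.

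**Conclusion.** The concern holds as a mismatch between test and design. The matched-data tests address change over time, and the phase question in both objectives gets a test that ignores the pairing. For within-woman correlations of 0.3 to 0.7, chi-square runs at about 0.6% to 3% instead of 5%. It gives up roughly 4 to 23 percentage points of power against mid-p or asymptotic McNemar (44.8% versus 49.1% at the low end, 43.2% versus 66.2% at the high end).

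These sizes rest on assumed incidences and correlations. If a woman's two teeth were uncorrelated, McNemar would gain nothing and lose about 2 points. The calculation also takes the outcome as yes/no, which Cochran's Q and McNemar both require. That the unpaired test does not fit paired data follows from the design and needs none of these assumptions.

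**What to change.** - Replace Chi-Square/Fisher with McNemar, mid-p or asymptotic and named in advance, comparing the menstrual and ovulatory restoration of the same woman for incidence at each time point.
- Keep Cochran's Q and the time-pair McNemar tests as descriptive only, outside the Bonferroni family for the phase comparisons.
- State that phase conclusions rest only on the direct paired comparison, and not on one phase being significant and the other not. Name the primary test and time point.
- If a difference in time course is of interest, test phase x time in one model that accounts for both woman and tooth within woman: random effects for both, or GEE clustered on woman with robust standard errors. A random effect for woman alone is not enough. In a linear check with no true effects, and with observations correlated 0.5-0.7 within a tooth and 0.3-0.4 between phases, such a model found a false phase effect in 10% to 24% of trials.

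The cost is analysis wording and at most one optional model, with no new data. The small downside is that a woman with one of her two restorations missing drops out of the McNemar comparison.

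### The comparison of the two cycle phases is assigned to tests for independent groups, although the same 35 women supply both groups

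*Combined protocol and SAP*

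**What the plan says.** Under Study Design the trial is a "Double-blind, split-mouth, randomized clinical trial" with "35 women, each receiving two restorations", giving "70 restorations" in all. The two study groups are the two cycle phases, menstrual (MPG) and ovulatory (OPG). The protocol does not say outright that each woman has one restoration in each phase, but a split-mouth design with two groups and two restorations per woman implies it.

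Under Statistical Analysis, Cochran's Q is assigned to comparisons within a group. "McNemar's test" follows as its post-hoc procedure. The "Chi-Square test or Fisher's Exact Test" is listed "for intergroup comparisons". Bonferroni correction and a 0.05 significance level complete the list. No paired test, clustered model or random effect is named for MPG versus OPG.

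**The concern.** Both objectives, on postoperative sensitivity and on rebound pain, ask whether the outcome differs between phases. That is the MPG-versus-OPG contrast, and it is made within women. Chi-Square and Fisher's exact test assume that the two groups contain different, independent subjects, so they use only the two marginal totals and discard which woman contributed which result.

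The plan respects repeated measurement where it compares time points within a phase (Days 1 to 3; Hours 4, 8 and 12) and ignores it where it compares phases. If a woman who has pain after one restoration tends to have it after the other, the unpaired standard error is too large. A real phase effect is then more likely to be reported as no difference, and the efficiency that a split-mouth design offers is given up.

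**Working it through.** **The plan's own figure.** 35 women × 2 restorations = 70, which agrees with the stated total. The number of independent units is 35. The documents contain no power calculation to reproduce, and no event rates or within-woman correlation.

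**Inputs.** n = 35 pairs and a 0.05 level come from the protocol. Two-sided testing, the incidences p1 and p2, and phi (the correlation between a woman's two binary outcomes) are assumptions, shown as ranges.

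**Standard error of p1 − p2**, with q = 1 − p:

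- treated as independent: √[(p1q1 + p2q2)/n]
- paired: √[(p1q1 + p2q2 − 2·phi·√(p1q1p2q2))/n]

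With both rates at 40%, the independent formula gives √(0.48/35) = 0.117 whatever phi is. The paired value is √(0.48 × 0.7/35) = 0.098 at phi 0.3 and √(0.48 × 0.5/35) = 0.083 at phi 0.5. With equal rates the ratio is 1/√(1 − phi): 1.20 at phi 0.3 and 1.41 at phi 0.5.

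**True level of the planned test.** In large samples this is 2·[1 − Φ(1.96/√(1 − phi))], which gives 1.9% at phi 0.3 and 0.6% at phi 0.5. Enumerating every possible paired table for n = 35, with both rates at 40%, gives these rejection rates:

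| phi | Chi-Square | Fisher | mid-p McNemar |
|---|---|---|---|
| −0.2 | 7.1% | 4.5% | 4.5% |
| 0 | 4.8% | 2.8% | 4.7% |
| 0.3 | 1.9% | 0.9% | 4.3% |
| 0.5 | 0.6% | 0.2% | 3.9% |

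**Power**, by the same enumeration:

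| Rates | phi | Chi-Square | Fisher | exact McNemar | mid-p McNemar |
|---|---|---|---|---|---|
| 50% vs 25% | 0 | 59% | 50% | 49% | 57% |
| 50% vs 25% | 0.2 | 60% | 49% | 57% | 66% |
| 50% vs 25% | 0.3 | 60% | 49% | 63% | 72% |
| 50% vs 25% | 0.5 | 61% | 48% | 81% | 88% |
| 40% vs 20% | 0.3 | 44% | 33% | 46% | 56% |
| 40% vs 20% | 0.5 | 42% | 30% | 60% | 72% |

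**One set of margins, three answers.** Suppose 18 of 35 restorations are painful in one phase and 10 of 35 in the other. Chi-Square = 70 × (18 × 25 − 10 × 17)² / (35 × 35 × 28 × 42) = 3.81, p = 0.051; Fisher gives p = 0.087. Neither depends on the pairing. Exact McNemar gives p = 0.096, 0.039 or 0.008 when the discordant pairs split 13/5, 10/2 or 8/0. The planned tests cannot tell these three datasets apart.

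**The case against.** The mismatch itself is hard to dispute; the case on the other side concerns its size.

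- **Correlation.** A positive within-woman correlation is an expectation. The two teeth are treated at different visits, and the documents give no estimate. At phi near zero the loss against Chi-Square disappears. This stands, and the figures above are conditional on it.
- **Choice of paired test.** Exact McNemar is itself conservative. At 50% versus 25% it has less power than Chi-Square up to phi 0.2 and gains only 3 points at phi 0.3 (63% against 60%). This stands, and it argues for mid-p McNemar or a clustered model over the exact test.
- **Best-case scenario.** With margins of 50% and 25%, phi cannot exceed 0.125/0.2165 = 0.577. At phi 0.5 the discordant cells are 26.7% and 1.7%, so 88% against 61% is close to the most that pairing can yield. The phi 0.3 row is the more cautious guide.
- **Direction of error.** With positive correlation the error is conservative and does not create false positives. That is true, but a missed effect on the primary contrast still matters, and a negative correlation would push Chi-Square above 5%.
- **McNemar is already named.** It could be read as covering the phase contrast. The text does not support this: the between-group comparison is expressly given to Chi-Square or Fisher, and McNemar follows Cochran's Q as its post-hoc step. That it applies only to time points is an inference from this placement, though the natural one.

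**Conclusion.** The concern holds. The planned between-phase test does not fit the split-mouth design, and it falls on the contrast behind both objectives. That conclusion rests on the text and needs no assumed rates; the standard error is wrong for any non-zero within-woman correlation.

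The size does rest on assumptions. For phi between 0.3 and 0.5 the standard error is 20% to 41% too large and the Chi-Square test runs at 1.9% to 0.6%. At 50% versus 25%, the power given up relative to mid-p McNemar is 12 to 27 points for Chi-Square and 23 to 40 points for Fisher. At phi 0 there is essentially no loss against Chi-Square. Since the documents contain no sample-size calculation, nothing shows that 35 pairs can absorb a loss of this kind. This must be fixed before analysis.

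**What to change.** Replace the between-group line with a within-woman analysis of MPG versus OPG:

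- For a binary sensitivity or rebound-pain outcome, use McNemar's test on the 35 pairs, preferably mid-p, and report the paired risk difference with its confidence interval.
- Alternatively, use conditional logistic regression or GEE clustered on woman, with a term for visit order, because the two phases are treated at different visits.
- If the 0–10 VAS is analysed as a score, use the Wilcoxon signed-rank test or a mixed model with a random effect for woman.
- Keep Chi-Square and Fisher only for comparisons between different women.

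The change itself is a line or two of SAP wording, with no new patients, visits or data. A binary analysis also needs a stated VAS cut-off and time point. The planned Chi-Square or Fisher test needs the same definitions and the documents do not give them, so this is an existing gap and not a cost of the change.

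### Bonferroni is valid here, but Holm's step-down procedure controls the same familywise error, never rejects less and sometimes rejects more

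*Combined protocol and SAP*

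**What the plan says.** The Statistical Analysis section of the combined protocol and SAP is a list of tests. Cochran's Q is given "for intragroup comparisons", "McNemar's test" "for post-hoc analysis", and chi-square or Fisher's exact test "for intergroup comparisons". The multiplicity line reads "Bonferroni correction" "for multiple comparisons", with significance at 0.05. It does not say which tests form the family or how many there are. No stepwise method and no confidence intervals are mentioned.

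Each outcome has three readings (Interventions & Procedures). For sensitivity the plan gives "VAS (0-10) measured at Day 1, Day 2, and Day 3 after restoration"; for rebound pain, "VAS (0-10) measured at Hour 4, Hour 8, and Hour 12 after anesthesia resolution". There are 35 women with two restorations each, and no sample-size calculation.

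**The concern.** Single-step Bonferroni holds every p-value to 0.05/m, where m is the number of tests in the family. Holm holds only the smallest p-value to that threshold and relaxes it after each rejection, at the same familywise error. The plan therefore uses a method that another dominates.

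The post-hoc step has a further inefficiency. With exactly three times, a significant Cochran's Q already protects the pairwise McNemar tests, so dividing alpha by three after it is more than familywise control requires.

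What is at stake is some power for the second and third comparisons in a small trial. The validity of any positive finding is not in question.

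**Working it through.** **Inputs from the documents.** Bonferroni; significance level 0.05 (two-sided assumed, since sidedness is not stated); three readings per outcome; 35 women. The plan states no adjusted alpha, m, power, effect size or event rate, so it has no figure to reproduce. Every effect and rate below is an assumption.

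**Step 1: thresholds.** Bonferroni uses 0.05/m throughout. Holm compares the ordered p-values with 0.05/m, 0.05/(m-1), ..., 0.05.
- m = 3: Holm 0.05/3 = 0.0167, 0.05/2 = 0.025, 0.05; Bonferroni 0.0167 throughout.
- m = 6: Holm 0.0083, 0.0100, 0.0125, 0.0167, 0.025, 0.05; Bonferroni 0.0083 throughout.

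Every Holm threshold is at least 0.05/m, so nothing that Bonferroni rejects is lost. The first threshold is the same for both, so at least one rejection occurs in exactly the same data sets.

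**Step 2: error control.** With m0 true nulls, the first true null that Holm could reject is met at a threshold of at most 0.05/m0. By Boole's inequality the familywise error is at most m0 × 0.05/m0 = 0.05, whatever the dependence. In 200,000 simulated runs per setting no Bonferroni rejection was missed by Holm, and Holm's familywise error was at most 0.0498 for m of 2 or more.

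**Step 3: size of the gain, generic tests.** Each test has 80% power at unadjusted 0.05; correlation 0. Power is per false null.

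| m | nulls false | Bonferroni | Holm |
|---|---|---|---|
| 2 | 2 | 0.712 | 0.775 |
| 3 | 3 | 0.658 | 0.750 |
| 3 | 1 | 0.657 | 0.659 |
| 6 | 6 | 0.565 | 0.683 |
| 6 | 1 | 0.565 | 0.566 |

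**Step 4: 35 pairs, three readings, paired t-tests** (20,000 runs; correlation 0.3-0.8).
- 0.5 SD at every reading: 67% v 74-76% per reading; all three shown in 38-53% v 58-68%.
- 0.6, 0.45 and 0.3 SD: power for the smallest effect 24-25% v 37-39%.
- Effect at one reading only: 67.2% v 67.4%.

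**Step 5: the between-phase test as named** (Fisher, 35 v 35, three times; latent correlation 0.6 between times and 0.5 between phases).
- 50/35/20% v 30/20/10%: power 15/7/3% becomes 15/8/4%.
- 50% v 25% at every time: about 30% becomes 35%.
- 60/45/30% v 30/20/10%: 50/33/24% becomes 52/40/33%.

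**Step 6: post-hoc McNemar after Cochran's Q.** Among three times, any two pairwise equalities imply the third. The only intersection hypothesis is therefore that all three are equal, which is what Q tests. Closed testing then allows each pair to be tested at 0.05 once Q is significant at 0.05. If all discordant women change in one direction, exact McNemar gives 2 × 0.5^6 = 0.031 with six and 2 × 0.5^7 = 0.0156 with seven. Seven are therefore needed at 0.0167 and six at 0.05, and the gated rule also needs Q to be significant.

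Simulation with exact McNemar, n = 35, latent correlation 0.5:
- Rates 50/30/15%: power for the three pairs 0.24/0.85/0.15 (Bonferroni), 0.32/0.85/0.21 (Holm), 0.41/0.93/0.29 (Q-gated). Any pair: 86%, 86%, 94%.
- Rates 30/20/10%: any pair 38%, 38%, 55%.

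**Step 7: does the gate hold its level?** With equal true proportions, Q alone ran at 0.050-0.051 under equal correlations between times, 0.056-0.059 with correlations 0.8/0.8/0.4, and up to 0.066 with 0.9/0.1/0.1. The familywise error of Q followed by exact McNemar at 0.05 was 0.035-0.044 in the global-null settings run, because exact McNemar is conservative.

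**The case against.** The strongest reply is that Bonferroni is valid and familiar, and that nothing in the plan is wrong because of it. That stands.

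The power figures in Step 4 come from paired t-tests, which the plan does not name, and from effects at every reading. For the named Fisher test with moderate effects (Step 5, first line) the gain is about one point or less per reading. It grows only when effects are large or present at every time. That also stands.

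A reader might infer that Bonferroni gives up power for nothing whatever family is chosen, or that Holm would make the trial more likely to find some phase difference. The documents support neither. With m = 1 the two methods coincide. For larger m the chance of at least one rejection is identical, and with one false null the gain is negligible. Bonferroni also brings simple simultaneous confidence intervals, which Holm lacks; this plan names no intervals, so that advantage is not used here.

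On the Q-gated rule, the objection that Q can be liberal under unequal correlations is correct for Q alone. The combined rule stayed below 0.05 in the settings run, but that is simulation evidence and not a guarantee. Holm on exact McNemar tests does not depend on it.

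Finally, the undefined family matters more than the choice of method: Bonferroni's threshold is 0.0167 at m = 3, 0.0083 at m = 6 and 0.0042 at m = 12. Switching to Holm does not settle that; the family must be written down as well.

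**Conclusion.** The point holds as an optional improvement. Holm's dominance over Bonferroni is a mathematical fact and needs no assumption about this trial.

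Its size does depend on assumptions. The gain is roughly 6 to 12 points per test when all nulls in a family of two to six are false and each test has 80% unadjusted power. It is about 1 to 9 points for the Fisher scenarios with effects at all three times, nearly nil when one null is false, and always nil for the chance of any rejection under Holm.

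The Q-gated McNemar step can raise the chance of any pairwise finding (86% to 94%, and 38% to 55%, at assumed rates), but it concerns changes over time within a phase and not the phase comparison in the objectives. All power figures are illustrative, because the documents give no effect sizes or event rates. It would be wrong to conclude that the planned correction is invalid or that the trial's main comparison is materially damaged by it.

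**What to change.** 1. Replace the Bonferroni line with Holm's step-down procedure for the between-phase tests at the three times, applied separately within each outcome. This also fixes the family at m = 3 per outcome, a choice that should be stated openly.
2. For the post-hoc time comparisons within a phase, choose one rule in advance: (a) exact McNemar for each of the three pairs at 0.05, only if Cochran's Q is significant at 0.05, with a permutation p-value for Q; or (b) Holm on the three exact McNemar tests. Permuting within women is exact only if the times are exchangeable, so it need not fully remove Q's liberality under unequal correlations. Option (b) needs no such condition and is the safer choice where that is a worry.
3. Report ordinary 95% confidence intervals beside the adjusted p-values, and say that they are not simultaneous.
4. If power figures are used to support the change, label them illustrative and state the assumed effects and tests.

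The cost is a few lines of analysis text, with no extra data. The one thing given up is Bonferroni's simple simultaneous intervals, which the plan does not use. The change should be recorded before the outcome data are analysed.
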